6.2 Statistical Methods

Baseline demographics

- Mean age - Wilcoxon rank sum
- AMA as categorical variable - chi2
- Race/ethnicity - Fisher exact
- Mean GA - Wilcoxon rank sum
- GA<14 wks as categorical - chi2
- Insurance status - Fisher exact
- Employed yes/no - chi2
- Education level - fisher exact
- Religion - Fisher exact
- Prior GC - chi2
- Planning invasive testing - Fishers exact
- Mean knowledge score on enrollment - Wilcoxon rank sum

Results

1. Compare control group following genetic counseling to intervention group following decision aid
 - Mean knowledge - Wilcoxon rank sum
 - Mean decisional conflict - Wilcoxon rank sum
 - Planned test - Fisher exact

2. Compare control group following genetic counseling to intervention group following decision aid and genetic counseling
 - Mean knowledge - Wilcoxon rank sum
 1. Represented in figure
 - Decisional conflict - Wilcoxon rank sum
 1. Represented in figure
 - Planned test - Fisher exact
3. Compare intervention group following decision aid to intervention group following both decision aid and genetic counseling
 - Mean knowledge - Wilcoxon signed rank
 1. Represented in figure
 - Decisional conflict - Wilcoxon signed rank
 1. Represented in figure
 - Planned test - descriptive (% changed)

No interim analyses are planned.

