1 BACKGROUND AND RATIONALE

Many different aneuploidy screening and diagnostic testing options are available to patients based on gestational age, all with different risks and benefits. Cell-free DNA screening has improved sensitivity and specificity for common aneuploidies¹ but likely reduced detection of other chromosomal abnormalities.² However, traditional screening such as first trimester screening, which have poorer detection characteristics for common aneuploidies, may be more likely to identify pregnancies other, less common, chromosomal abnormalities.² Diagnostic testing choices include chorionic villus sampling and amniocentesis, both of which carry a low risk of pregnancy loss of approximately 1 in 455 to 1 in 900 respectively.³ Counseling on screening and testing options is recommended by the American College of Obstetrics and Gynecology for all women, ideally at the first prenatal visit.⁴ Additionally, recommendations by the American College of Medical Genetics emphasize the importance of appropriate pretest counseling for patients undergoing prenatal screening with cell-free DNA.⁵

This increasing number of screening modalities complicates prenatal counseling for prenatal care providers and can be difficult for patients to understand, especially patients with low health literacy.⁶ While many patients may be aware of trisomy 21, many have never heard of other aneuploidies and may be unfamiliar with the basic principles of genetic screening and prenatal aneuploidy detection.

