1.1 Description of Intervention

A decision aid incorporating all aneuploidy screening and diagnostic testing options available at the time of the study was developed with input from maternal fetal medicine physicians, a geneticist, and genetic counselors. This was designed within a tablet-based application. The decision aid was also translated into Spanish by a single translator and the translation reviewed by a second native Spanish speaker. The language was simplified to a 10th grade reading level on the Flesch-Kincaid scale. Completion of the decision aid takes approximately 20 minutes. Information surrounding patient age and gestational age are incorporated to guide the study participant toward available options.

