3.4 Study Population

English and Spanish-speaking women with a singleton gestation at less than 22 weeks who are scheduled to meet with a genetic counselor at one of three prenatal diagnosis clinics for a discussion of aneuploidy screening and testing options are eligible for participation.

Exclusion criteria include: multiple gestations, prior abnormal ultrasound in the current pregnancy, or prior aneuploidy screening in the current pregnancy.

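### The between-arm comparison of planned test ignores gestational age, so percentages for any gestation-limited test include women who could not choose it

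*Combined protocol and SAP*

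**What the plan says.** The synopsis lists the test chosen among the secondary objectives, and section 2.2 lists choice of testing as a secondary outcome.

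Section 6.2 sets three comparisons. Results 1 (control after counseling versus intervention after the aid) and Results 2 (control after counseling versus intervention after aid and counseling) each analyze test choice with the line "Planned test - Fisher exact". Neither gives a stratum, a restriction, a denominator rule or a list of test categories. Results 3 compares the intervention group with itself before and after counseling, and for planned test gives only the percentage who changed.

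Gestational age enters section 6.2 only under baseline demographics, as a mean and as "GA<14 wks as categorical - chi2".

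On availability, section 1 states: "Many different aneuploidy screening and diagnostic testing options are available to patients based on gestational age". It names "traditional screening such as first trimester screening" among them. Section 1.1 says of the aid: "Information surrounding patient age and gestational age are incorporated to guide the study participant toward available options". Section 3.4 admits women with a "singleton gestation at less than 22 weeks". Section 3.1, in a paragraph on counseling, cost and insurance, says that within professional guidelines every screening test is open to every woman; it does not mention gestational age.

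**The concern.** If options depend on gestational age and enrollment runs to 22 weeks, one pooled table mixes women who faced different sets of options. On the wording of sections 1 and 1.1, a woman enrolled at 20 weeks would count in the denominator for first trimester screening. The percentage reported for that test would then reflect the gestational-age mix of the sample as well as women's preferences, and an effect of the aid on that test would look smaller than it was among the women who could act on it.

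What is at stake is the interpretation of a secondary outcome. A reader might conclude that the aid barely moved a test when it moved it appreciably among those eligible. The plan already defines a gestational-age category and section 5 already collects gestational age, so the information needed to prevent this is in hand.

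**Working it through.** **Stated figures.** The plan gives no expected percentages, effect or power for planned test, so there is no figure of its own to reproduce on this point. The 92 per arm in section 6.1 belongs to the knowledge endpoint. It is borrowed here only as the number of evaluable women (92 / 0.925 = 99.5, the plan's 100 enrolled per arm). Whether 92 is right for knowledge is a separate question.

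**Direction.** Let f be the share of women who can have a given test, and p1 and p2 its uptake among those women in the two arms, with no uptake among the rest. Then:

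- pooled percentages are f·p1 and f·p2;
- the pooled absolute difference is f·(p1 − p2), which shrinks by the factor f;
- the pooled ratio is f·p1 / (f·p2) = p1 / p2, which is unchanged.

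If a test is open to everyone, f = 1 and nothing shrinks.

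**Illustrative size.** All of the following are assumptions, not document figures: p1 = 50%, p2 = 25%, 92 per arm, f equal to the share under 14 weeks, and a yes/no comparison for one test. Power is by exact enumeration of Fisher's test at two-sided 0.05. The restricted analysis uses 92·f women per arm, rounded.

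| f | Pooled percentages | Pooled difference | Power, pooled (92 per arm) | Power, restricted (n per arm) |
|---|---|---|---|---|
| 0.3 | 15% vs 7.5% | 7.5 points | 28% | 39% (28) |
| 0.5 | 25% vs 12.5% | 12.5 points | 52% | 62% (46) |
| 0.7 | 35% vs 17.5% | 17.5 points | 73% | 80% (64) |
| 0.9 | 45% vs 22.5% | 22.5 points | 88% | 89% (83) |

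With 40% versus 60% uptake instead, the pairs are 29% vs 39% (f = 0.5), 46% vs 54% (f = 0.7) and 63% vs 69% (f = 0.9). The gap closes as f approaches 1.

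**Validity.** With the same 28% in both arms and 92 per arm, the exact rejection rate of the pooled Fisher test is 0.033, below 0.05.

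**Chance imbalance.** Section 3.2 describes a coin flip without stratification. The between-arm gap in the share under 14 weeks has standard deviation √(2f(1 − f)/92): 7.4 points at f = 0.5, 6.8 at 0.7 and 4.4 at 0.9. This is ordinary random variation, but it does move the raw percentages.

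**Multi-category form.** Planned test is more naturally one variable with several categories. In simulations under assumed rates with 92 per arm, a generalized Cochran-Mantel-Haenszel test stratified at 14 weeks kept type I error near 5%. It gained about 1 to 8 points of power over the pooled test when the aid shifted an early-only test, and lost no more than about 1 point when the shift was to a test open at all gestations.

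**The case against.** The strongest case for leaving the plan alone has four parts.

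*The pooled comparison answers a legitimate question.* It gives the aid's effect on choices across everyone enrolled; randomization keeps it valid, and the baseline table will show any gestational-age imbalance. This stands. It is the reason to keep the overall percentages, but it does not make them a description of choice among women who had the choice.

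*Stratifying can cost power.* That depends on the method. Adding up separate stratum chi-squares did lose power in one illustrative case (77% pooled versus 72%, with half of women under 14 weeks and a shift to an unrestricted test). The generalized Cochran-Mantel-Haenszel test loses about 1 point at most, so the method should be named.

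*Section 3.1 says all screening tests are open to all women, and nowhere is 14 weeks called an availability boundary.* Both observations stand. Section 3.1 covers screening tests only and is silent on gestation, whereas section 1 covers screening and diagnostic options. Read literally for every gestation, it would conflict with sections 1 and 1.1. The documents need reconciling, and 14 weeks is a cut to be confirmed.

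*The size is hypothetical.* This also stands: neither the share under 14 weeks nor any choice rate is given.

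A reader might go further and infer that every planned-test difference is diluted, that the pooled test or the unstratified coin flip makes the comparison invalid, or that the percentage changed in Results 3 is diluted too. The documents support none of these. No section limits cell-free DNA to one side of 14 weeks, and a test open throughout is not diluted by this route. The pooled test does not inflate type I error. Results 3 is within-woman and descriptive, so it has no between-arm difference to dilute.

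**Conclusion.** The concern holds in a limited form. For any test whose availability depends on gestational age, Results 1 and 2 will report percentages whose denominators include women who could not choose it, and the absolute between-arm difference will be reduced by the factor f. Relative differences and tests open at every gestation are not affected.

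The loss cannot be sized from the documents. Under the assumed 50% versus 25% uptake it is about 7 to 11 points of exact Fisher power for f between 0.3 and 0.7, and under 2 points at f = 0.9. These figures also assume no uptake outside the eligible group and a single yes/no comparison. Because the outcome is secondary and the primary conclusion is untouched, this is a change the sponsor should make because it is cheap and clarifies the result; it does not threaten the trial.

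**What to change.** 1. In section 6.2, Results 1 and 2, compare planned test with a generalized (multi-category) Cochran-Mantel-Haenszel test or a stratified exact test, stratified by the existing category of under 14 versus 14 weeks or more.
2. Report test percentages by arm within each stratum. For a gestation-limited test, restrict the denominator to women for whom it was available. Overall percentages can stay alongside.
3. State which tests were available at which gestational ages, confirm whether 14 weeks is the boundary, and reconcile section 3.1 with sections 1 and 1.1. Step 2 cannot be carried out until this is done.
4. For Results 3, showing the percentage changed by stratum is optional; women with fewer options may have had less scope to change.

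Cost: SAP wording and a few more table rows. Gestational age is already collected. The downsides are smaller cells within strata and, if the aid acts only on tests open at all gestations, about 1 point less power in the illustrative simulation.

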A computerized decision aid was developed within a tablet-based application, available in Spanish and English, at a 10th grade reading level, to aid in patient education surrounding aneuploidy screening and testing options

Study Design

Unmasked randomized controlled trial

Subject Population

Inclusion Criteria

key criteria for Inclusion and Exclusion:

- English and Spanish-speaking pregnant women
- Undergoing genetic counseling for indication of aneuploidy screening
- Ages 18-50

Exclusion Criteria

1. Multiple gestation
2. Prior aneuploidy screening in current pregnancy
3. Prior abnormal ultrasound in current pregnancy

Number Of Subjects

200

Study Duration

Each subject's participation will last for the duration of the study visit (approximately 45 minutes).

The entire study is expected to last 12 months.

Study Phases

Screening (1) Screening: Women scheduled for genetic counseling for indication of aneuploidy screening will be approached regarding eligibility and willingness to participate prior to their scheduled appointment.

Study Treatment

Follow-Up (2) Intervention: Participants will be randomized either to use the above-described decision aid prior to genetic counseling or to genetic counseling alone.

(3) Follow-up: None after study visit

Efficacy Evaluations

(1) Knowledge: A 12 question modification of the MSSKQ questionnaire will be used to assess knowledge

(2) Decisional conflict: A validated low-literacy decisional conflict scale will be used to assess decisional conflict

Pharmacokinetic Evaluations N/A

Safety Evaluations N/A

Statistical And Analytic Plan

(1) Primary outcome: Noninferiority of knowledge will be assessed graphically and with Wilcoxon Rank-Sum

(2) Secondary outcomes: knowledge and decisional conflict scores will be assessed with Wilcoxon Rank-Sum

DATA AND SAFETY MONITORING PLAN Participants were provided with contact information for the PI should they have any concerns. No safety concerns are anticipated.

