2 STUDY OBJECTIVE

2.1 Primary Objective

The primary hypothesis of this study was that knowledge scores of women in group 2 following completion of the decision aid only would not be inferior to knowledge scores of women in group 1 following genetic counseling. A noninferiority limit of 1 question different on a 12 point questionnaire was selected as a clinically relevant difference.

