4.2 Intervention

Following informed consent, the app was accessed and a study ID assigned. Via a coin-flip algorithm within the app, women were randomly assigned to group 1 (control group) or group 2 (decision aid group). As it was not pragmatic for this study, randomization assignment was not blinded. Investigators were not involved in developing the randomization scheme within the app. All women completed an initial demographic and knowledge questionnaire immediately following randomization via self-administered assessments within the app.

Study flow is described in the below figure. Women randomized to group 1 met with the genetic counselor as scheduled, then completed the knowledge and decisional conflict assessments. Women randomized to group 2 self-administered the decision aid within the app, then completed the knowledge and decisional conflict assessments. Following this, they met with the genetic counselor as scheduled; following this appointment, they again completed the same assessment.

Additionally, prior to and following meeting with the genetic counselor, women in group 2 were asked whether they would or did find it helpful to meet with a genetic counselor.

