4.3 Subject Completion/ Withdrawal procedures

Participants are instructed to inform their enrolling research study personnel should they desire to withdraw and participation could be terminated at that time.

5 STUDY EVALUATIONS AND MEASUREMENTS (how measurements will be made)

- Demographic characteristics will be abstracted from questionnaires and medical chart
 - o Age
 - o Race/ethnicity
 - o Preferred language
 - o Parity
 - o Gestational age
 - o Site of enrollment
 - o Insurance status
 - o Employment status
 - o Education level
 - o History of genetic counseling in prior pregnancy
- Baseline knowledge assessment
 - o This will be assessed via the previously described modified MSSKQ questionnaire prior to intervention
- Knowledge and decisional conflict scores as described will be collected via self-administered questionnaires embedded within the application

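### Baseline knowledge is measured in every woman but left out of the primary comparison; adjusting for it is a cheap efficiency gain of unknown size, not a correction of an invalid analysis

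*Combined protocol and SAP*

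**What the plan says.** Baseline knowledge is collected from everyone. Section 4.2 states: "All women completed an initial demographic and knowledge questionnaire immediately following randomization". Section 5 says of the baseline assessment: "This will be assessed via the previously described modified MSSKQ questionnaire prior to intervention". It is therefore the same instrument as the outcome, taken before either form of education.

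Section 6.2 uses this score once, in the list of baseline comparisons: "Mean knowledge score on enrollment - Wilcoxon rank sum". The primary comparison, Results item 1 (control after counseling against intervention after the decision aid), reads "Mean knowledge - Wilcoxon rank sum". The synopsis agrees: "Noninferiority of knowledge will be assessed graphically and with Wilcoxon Rank-Sum". No regression, ANCOVA, change-from-baseline analysis or stratified rank test is listed. The signed-rank tests in Results item 3 compare two post-intervention time points within group 2 and do not use baseline.

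The yardstick is in section 2.1: "A noninferiority limit of 1 question different on a 12 point questionnaire was selected". On masking, section 4.2 says: "As it was not pragmatic for this study, randomization assignment was not blinded".

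**The concern.** A noninferiority claim depends on the width of the interval for the group difference relative to the limit. If women who know more at baseline also score higher afterwards, part of the spread in post-intervention scores is predictable, and removing it narrows the interval without recruiting anyone else. The score is already in hand, so leaving it out may waste information.

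The plan also tests for a baseline difference between arms without saying what would follow from one. Fixing the model in advance removes that choice from an unblinded analysis.

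What is at stake is the chance of reaching a conclusion, not the correctness of the conclusion reached.

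**Working it through.** **Inputs.** From the documents: limit 1 question (2.1); SD 3, 92 evaluable women per arm, two-sided alpha 0.05, hence one-sided 0.025 for noninferiority (6.1). Assumed: true difference 0; equal SDs at baseline and after the intervention; SD 3 is not already baseline-adjusted (6.1 does not describe it as such). Not given: r, so a range is shown. Differences are group 2 minus group 1, so the limit is -1.

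**The plan's own figure.** With limit 1 and SD 3, n per arm = 2 × (1.960 + 0.842)² × 3² / 1² ≈ 141.3, that is 142, not 92. The allowance for fall-out does reproduce: 92 / (1 - 0.075) = 99.5, that is 100. The mismatch over 92 is a separate issue. It matters here only because it sets the starting power at 61%.

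**Gain from adjustment.** Residual SD = 3 × √(1 - r²). Standard error = residual SD × √(2/92). Half-width = t(0.975) × standard error, with 182 degrees of freedom unadjusted and 181 adjusted. Power is from the noncentral t distribution with noncentrality 1 / standard error. For example, unadjusted: 3 × √(2/92) = 0.442, half-width 0.873, power 0.614. At r = 0.5: residual SD 2.598, standard error 0.383, half-width 0.756, power 0.738.

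| r | 95% half-width | Power (formula) | Power (simulated ANCOVA, robust SE) |
|---|---|---|---|
| unadjusted | 0.873 | 0.614 | 0.61 (unadjusted interval) |
| 0 | – | – | 0.602 |
| 0.1 | 0.868 | 0.618 | 0.605 |
| 0.2 | 0.855 | 0.631 | 0.622 |
| 0.3 | 0.833 | 0.654 | 0.644 |
| 0.5 | 0.756 | 0.738 | 0.729 |
| 0.6 | 0.698 | 0.803 | 0.797 |

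The simulations used 20,000 trials per setting. A gain of 5 points needs r of about 0.33, 10 points about 0.46, and 80% power about 0.596. At r = 0, adjusting costs about one point.

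**Possible bias.** Suppose knowing the assignment lowered group 2 baseline answers by d questions and left post-intervention scores unchanged. The adjusted difference then moves by r × d towards noninferiority. With an assumed d = 0.5 the shift is 0.10, 0.15 and 0.25 question at r = 0.2, 0.3 and 0.5. At a true difference of -1, false noninferiority becomes 0.042, 0.054 and 0.095 by formula (0.043, 0.054 and 0.090 simulated). The unadjusted comparison stays at 0.024 to 0.027. With no shift, ANCOVA keeps 0.024 at r = 0.3 and 0.5.

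**Requiring the two intervals to agree.** Simulated at a true difference of 0, both intervals lie above -1 in about 58 to 59% of trials at r = 0.3 to 0.6, slightly below the 61% for the unadjusted interval alone. At r = 0.5 about one in five ANCOVA successes lacks support from the unadjusted interval. The two estimates differ by chance alone with an SD of 0.22 at r = 0.5, so a gap of 0.25 between them does not by itself show bias.

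**The case against.** The strongest case for leaving the plan alone has three parts.

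First, the benefit rests on a number nobody has shown. Section 1 says that many patients "may be unfamiliar with the basic principles of genetic screening and prenatal aneuploidy detection", and both arms are then taught that content, so r could be low. This stands: the documents do not show that a material gain is likely.

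Second, ANCOVA brings in a covariate answered after randomization in an unblinded trial, whereas the unadjusted comparison is immune to any change in baseline answers. The larger r is, the larger both the gain and the possible bias. On this view the adjusted analysis belongs in a supporting role. The downside is real and has to be stated, but the shift is hypothetical. A reader might infer that women already knew their group when they answered. Section 4.2 says only that assignment was unblinded and that the questionnaire followed randomization; it does not say that the assignment was displayed first. Nor do the documents show any effect on the answers.

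Third, the 61% belongs to a mean-difference interval that the plan does not list, and starts low because of the sample-size mismatch. That is correct. Comparing an interval with the limit needs no covariate, and neither that improvement nor the shortfall in 92 per arm should be credited to this point.

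A tempting safeguard is to call the claim not robust whenever the adjusted and unadjusted intervals disagree about -1. Every success gained only through adjustment would then carry that label, which undoes the benefit.

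**Conclusion.** The point holds as a modest efficiency recommendation. Baseline knowledge is available for every woman, the primary comparison ignores it, and using it costs almost nothing. At 92 per arm with SD 3, limit 1 and true difference 0, power rises from 61% to 65%, 74% and 80% at r = 0.3, 0.5 and 0.6. At r of 0.2 or less the gain is two points at most. Confidence is medium because r is unknown.

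A reader might infer that the unadjusted comparison is biased or invalid. It is not: randomization supports it, and it matches the hypothesis in 2.1. A reader might also infer that adjustment would restore the intended 80% power. That needs r of about 0.6, for which the documents offer no evidence. The rise in false noninferiority to about 4%, 5% and 9% at r = 0.2, 0.3 and 0.5 depends wholly on the assumed 0.5-question shift.

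**What to change.** Before outcome data are examined, amend 6.2 Results item 1 and the matching synopsis line:

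- Primary estimate: the group difference in post-intervention knowledge from a linear model with group and baseline knowledge (ANCOVA) and robust standard errors. Compare its two-sided 95% confidence interval with -1.
- Prespecified sensitivity analyses: the unadjusted mean difference with its 95% interval, and the rank sum.
- Report baseline scores by arm, and state whether the app showed the assignment before the baseline questions.
- Do not make the claim conditional on agreement between the adjusted and unadjusted intervals.

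If enrolment has not begun, give the baseline questionnaire before the coin flip; this removes the risk of bias through the covariate. Sections 4.1 and 4.2 are written in the past tense, so that option may be gone. The same doubt applies to changing the primary analysis: if outcomes have already been examined, the adjusted result should be presented as supportive and post hoc.

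The cost is wording only, with no extra women or data. In exchange, a model-based mean difference replaces a rank test as primary, the covariate carries the possible bias described above, and about one point of power is lost if r is near 0.

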PROTOCOL TITLE: Use of a computerized decision aid for prenatal aneuploidy screening

Short Title: Aneuploidy decision aid

Lead Investigator:

[name].

University of North Carolina at Chapel

Version Date: January 3, 2018

NCT number: 02991729

TABLE OF CONTENTS

Table of Contents	2
Abbreviations and Definitions of Terms	3
Protocol Synopsis	4
1 BACKGROUND AND RATIONALE	7
2 STUDY OBJECTIVES	9
3 INVESTIGATIONAL PLAN	10
4 STUDY PROCEDURES	12
5 STUDY EVALUATIONS AND MEASUREMENTS	14
6 STATISTICAL CONSIDERATIONS	15
10 DATA COLLECTION AND MANAGEMENT	17
14 REFERENCES	18

ABBREVIATIONS AND DEFINITIONS OF TERMS

Abbreviation	Definition
MSSKQ	Maternal serum screening knowledge questionnaire
cfDNA	Cell-free DNA screening

PROTOCOL SYNOPSIS

Study Title	Use of a Computerized Decision Aid for Prenatal Aneuploidy Screening
--------------------	--

Funder	
• National Center for Advancing Translational Sciences (NCATS), NIH, Grant #UL1TR001111• UNC Department of OBGYN Cefalo-Bowes Grant (internal funding)
---------------	---

Clinical Phase	Phase II
-----------------------	----------

Study Rationale	
• All women should be offered aneuploidy screening or testing in each pregnancy• Screening and testing options are complex• Decision aids have been shown to improve knowledge and decrease decisional conflict with healthcare decisions, including aneuploidy screening• Prior decision aids which have been evaluated for aneuploidy screening did not include the newest screening option of cell-free DNA
------------------------	---

Study Objective(s)	
Primary
 
• To evaluate whether use of the computerized decision aid is noninferior than an abbreviated visit with a genetic counselor in increasing patient knowledge 
Secondary
 
• To evaluate whether use of the computerized decision aid is noninferior than an abbreviated visit with a genetic counselor in
---------------------------	--

decreasing patient decisional conflict

- To evaluate whether use of the decision aid in addition to genetic counseling improves patient knowledge and decisional conflict over genetic counseling alone
- To examine test chosen for aneuploidy screening

Test Article(s)

(If Applicable)

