2.2 Secondary Objective

Secondary outcomes included decisional conflict following decision aid completion, decisional conflict following decision aid completion and genetic counseling, change in knowledge score after genetic counseling in women who used the decision aid, choice of testing, and pursuit of invasive testing with high risk results.

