3.2 Allocation to Treatment Groups and Blinding (if applicable)

Via a coin-flip algorithm within the decision aid application, women will be randomly assigned to group 1 (control group) or group 2 (decision aid group)

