6 STATISTICAL CONSIDERATION

6.1 Sample size calculation

An initial power calculation was performed using historical data from the maternal serum screening questionnaire assuming a standard deviation of 3 questions; to achieve 80% power with a 2-tailed alpha of 0.05, 92 women would be needed in each arm. Assuming a 7.5% fall-out rate from women with nonviable pregnancies, 100 patients were required in each arm for a total enrollment of 200 women.

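### Section 6.2 records the baseline plan for invasive testing but leaves it out of the planned-test comparisons, which yield a valid p-value with no effect size, direction or confidence interval

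*Combined protocol and SAP*

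**What the plan says.** The Protocol Synopsis gives the secondary objective as "To examine test chosen for aneuploidy screening". Section 2.2 lists among the secondary outcomes "choice of testing, and pursuit of invasive testing with high risk results".

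Section 6.2 handles the planned test in three places:

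- **Results 1** (control after counseling against intervention after the aid): "Planned test - Fisher exact".
- **Results 2** (control after counseling against intervention after aid and counseling): the same test.
- **Results 3** (intervention arm only, from after the aid to after counseling): "Planned test - descriptive (% changed").

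Under baseline demographics, 6.2 also has "Planning invasive testing - Fishers exact". No other use of that answer is described. Section 6.2 gives no effect measure, confidence interval, stratification or category list for the planned test.

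The baseline items in Section 5 do not include a plan for invasive testing. Section 4.2 describes the entry data this way: "All women completed an initial demographic and knowledge questionnaire immediately following randomization". Allocation is by simple randomization (Section 3.2): "Via a coin-flip algorithm within the decision aid application, women will be randomly assigned".

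**The concern.** A woman's plan on arrival may well predict her plan later in the same visit. If it does, a comparison that ignores it carries avoidable noise. Coin-flip allocation does not balance the arms on this answer, and a baseline p-value adjusts nothing.

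A Fisher p-value is also a thin summary of a choice among tests. If the table has several categories, a small p-value does not show whether women moved between screening tests or toward or away from diagnostic testing. Section 1 separates those two kinds of test and notes a low pregnancy-loss risk with the diagnostic ones, so invasive yes or no is a contrast readers will want. Results 3 does not fill the gap: it starts after the aid rather than at baseline, and has no control counterpart.

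At stake are the precision and readability of one secondary outcome. The primary knowledge comparison is unaffected.

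**Working it through.** **Inputs from the documents.** Section 6.1 states "to achieve 80% power with a 2-tailed alpha of 0.05, 92 women would be needed in each arm". That figure was set for knowledge; no size or power is stated for the planned test, so there is no plan figure to reproduce here. I take n = 92 per arm.

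**Assumed inputs (not in the documents).** 10% plan invasive testing at baseline. Setting A: 40% of them keep the plan and 5% of the others adopt it. Setting B: 70% keep and 3% adopt. The effect case adds 10 points to adoption in the intervention arm.

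**Formulas.** Per-arm total variance is p(1−p), with p = 0.1·keep + 0.9·adopt. Within-stratum variance is 0.1·keep(1−keep) + 0.9·adopt(1−adopt). The variance ratio, stratified to unadjusted, is the sum over arms of the second divided by the sum of the first. With an effect confined to one stratum, add 0.1·0.9·0.10²/2 = 0.00045 to the numerator, because the stratum effects differ.

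**No effect.**
- A: p = 0.085. Total 0.085·0.915 = 0.0778; within 0.1·0.4·0.6 + 0.9·0.05·0.95 = 0.0668. Ratio 0.86, a 14% reduction.
- B: p = 0.097. Total 0.097·0.903 = 0.0876; within 0.1·0.7·0.3 + 0.9·0.03·0.97 = 0.0472. Ratio 0.54, a 46% reduction.

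**10-point rise among women without a baseline plan.**
- A: intervention p = 0.04 + 0.9·0.15 = 0.175, total 0.1444, within 0.1388. Ratio (0.0668 + 0.1388 + 0.00045)/(0.0778 + 0.1444) = 0.2060/0.2222 = 0.93, about a 7% reduction.
- B: intervention p = 0.07 + 0.9·0.13 = 0.187, total 0.1520, within 0.1228. Ratio (0.0472 + 0.1228 + 0.00045)/(0.0876 + 0.1520) = 0.1704/0.2396 = 0.71, about a 29% reduction.

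**As confidence intervals.** The 95% half-width is 1.96·√(summed variance/92).

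| Setting | Unadjusted | Stratified |
|---|---|---|
| A, no effect | 8.1 points | 7.5 points |
| B, no effect | 8.6 points | 6.3 points |
| A, 10-point rise | 9.6 points | 9.3 points |
| B, 10-point rise | 10.0 points | 8.4 points |

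**Dependence on the correlation.** With phi the correlation between baseline and later plan, the standard error ratio is √(1−phi²): 0.995 at 0.1, 0.954 at 0.3, 0.866 at 0.5 and 0.714 at 0.7. Settings A and B correspond to phi of about √0.142 = 0.38 and √0.461 = 0.68 under no effect.

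**Power by simulation** (4,000 trials per setting, 10-point rise, only the invasive category shifting). A four-category chi-square test, standing in for a Fisher test over all categories, had about 28% to 30%. The other tests gave:

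| Setting | Fisher, yes/no | Unadjusted score test | Stratified |
|---|---|---|---|
| A | 37% | 45.5% | 48.6% |
| B | 33% | 40% | 56% |

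So stratification itself adds about 3 points in A and 16 in B. The rest of the gain over Fisher comes from Fisher's conservatism: about 8 of the 11 to 12 points in A.

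**The case against.** The strongest reply is that nothing here is invalid. Allocation is randomized, and the standard error of an unadjusted comparison already allows for chance imbalance. A reader might infer that imbalance in the baseline plan biases the Fisher comparison; it does not. It costs precision only. This part of the objection stands.

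A reader might also infer that the objective asks whether invasive plans changed, and that the plan fails to answer it. The objective is only to examine the test chosen. It is secondary and unpowered, and the one invasive outcome in Section 2.2 concerns women with high-risk results. The gap lies in the listed analyses, not the data: a simple invasive yes/no comparison could still be made if the planned-test item identifies invasive tests.

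It may be tempting to put an invasive contrast in place of the overall comparison. The Synopsis and Section 1 motivate the aid by the arrival of cell-free DNA screening, and a shift between that and traditional screening would be invisible in such a contrast. The lower power of the multi-category test arises because the simulation moves only the invasive category. That the Fisher test spans all categories is itself an inference, since 6.2 defines none.

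Finally, the baseline item is barely described: Section 4.2 calls the entry questionnaire demographic and knowledge, and Section 5 omits the item. That stands, and is a reason to specify the item. None of this explains leaving out an estimate and interval, or leaving unused an answer that 6.2 already analyses.

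**Conclusion.** The planned-test comparisons are valid but less precise and less informative than the listed data permit. The missing effect size, direction and interval follow directly from the text of 6.2.

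The precision loss cannot be sized from the documents. Under the assumed rates, stratification removes about 14% to 46% of the variance under no effect and about 7% to 29% under the 10-point rise; with a correlation near 0.1 it removes almost nothing. The documents do not support saying that a real shift would probably be missed, and the stratified analysis does not cure low power: it reaches only about 48% to 56% in these settings.

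This is a worthwhile, inexpensive improvement to a secondary outcome. It does not threaten the trial's main conclusion.

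**What to change.** In Section 6.2, Results 1 and 2:

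- Keep the Fisher comparison, define the planned-test categories, and report the full table by arm with percentages.
- Add one supplementary estimate: the risk difference for invasive (diagnostic) test planned, yes against no, with 95% CI, by Mantel-Haenszel stratified on the baseline invasive-plan answer.

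In Section 5, add that answer to the baseline list and state that it is asked before the aid or counseling.

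The cost is protocol wording and a few lines of code. No new data are needed if the item is collected as 6.2 implies.

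There are two small drawbacks. The baseline-invasive stratum may be small: at the assumed 10% it is about 9 women per arm (0.10 × 92). Mantel-Haenszel weighting copes with that. And if the item belongs to the entry questionnaire, it is answered after unblinded randomization, though before the intervention, so knowledge of the assignment could color the answer. The report should say so.
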